3 GENERAL CONSIDERATIONS

3.1 General Methods

This statistical analysis plan (SAP) is for the purpose of the interim analysis which will use data collected in the placebo-controlled (PC) and open label extension (OLE) periods once all subjects have completed the PC period. It covers the analyses for the OLE portion of the study and analyses across both the PC and the OLE periods. The analysis for the PC period is documented in a separate 251PP301 placebo-controlled SAP. The analyses of selected exploratory endpoints may be documented separately. Since the objectives and endpoints given in Section 2 are taken directly from the protocol which covers both PC and OLE periods, only analyses relevant to the OLE

period which will have sufficient data at the time of the interim analysis will be presented in this SAP.

Summary tables will be presented using descriptive summary statistics. For continuous variables, summary statistics will generally include: number of subjects with data, mean, standard deviation, median, 25% percentile, 75% percentile, minimum and maximum. For categorical variables, this will generally include: number of subjects randomized or dosed, number with data, and the percent of those with data in each category.

Unless otherwise specified, change from baseline will be defined as post-baseline value minus baseline value. See Section 3.3 for the definition of baseline.

Unless stated otherwise, all statistical tests will be 2-sided with statistical significance level of 0.05.

The statistical software, SAS® will be used for all summaries and analyses.

The health care region used in the analysis (referred as region in this SAP) is defined as:

- US: United States
- Non-US: Australia, Austria, Canada, France, Germany, Greece, Italy, Russian, Spain, United Kingdom, Japan and Korea

The term “subject” is the equivalent to “participant” used in the protocol.

This OLE period analysis plan does not include listings since they are provided in the placebo-controlled period analysis (please refer to the 251PP301 placebo-controlled SAP). These listings will include all data in the placebo-controlled and OLE periods (all data in the study), with an indicator of the study period (screening, placebo-controlled, or OLE) for each record to indicate when the event occurred.

3.2 Population

- Dosed subjects: enrolled subjects who received at least one dose of study therapy, i.e., blinded therapy (BIIB092 or placebo) or open-label BIIB092. This is the same as the “Treated participants” in Section 17.2 of the protocol.
- Intent-to-treat (ITT) population:
The intent-to-treat population is defined as all randomized subjects who received at least one dose of blinded study treatment (BIIB092 or placebo).
- Safety population: all randomized subjects who received at least one dose of study treatment (BIIB092 or placebo).
- Efficacy MRI population: the subset of the ITT population who had a least one measurable brain volumetric measurement.
- Safety MRI population: the subset of the safety population who had a least one post-baseline safety MRI.
- Serum PK analysis population: the subset of the safety population who had at least one measurable post-baseline BIIB092 concentration in serum.

- CSF PK analysis population: the subset of the safety population who had at least one measurable post-baseline BIIB092 concentration in CSF.
- CSF PD analysis population: the subset of the safety population who had both baseline and at least one measurable post-baseline N -terminal tau CSF sample.
- Anti-drug antibody (ADA) analysis population: the subset of the safety population who had at least one post-dose sample evaluable for ADA.

OLE treatment groups for analyses

Analyses for efficacy data will be displayed by the following treatment groups according to randomization assignment at the start of the placebo-controlled period:

- BIIB092 early start: subjects who are assigned to (1) receive BIIB092 in the placebo-controlled period and (2) continue receiving BIIB092 in the OLE period
- BIIB092 late start: subjects who are assigned to (1) receive placebo in the placebo-controlled period and (2) switch to BIIB092 in the OLE period

Unless otherwise specified, analyses for safety, PK, and ADA data will be displayed by the following treatment groups according to dose received:

- BIIB092 early start: subjects who receive BIIB092 in the placebo-controlled period (regardless of randomization assignment)
- BIIB092 late start: subjects who receive only placebo in the placebo-controlled period (regardless of randomization assignment) and switch to receive BIIB092 in the OLE period
- BIIB092 total: subjects in either BIIB092 early or late start treatment groups

If all subjects received study treatment according to their randomization assignments during the placebo-controlled period (i.e. no subject assigned to placebo received BIIB092, and no subject assigned to BIIB092 received only placebo) then the assignment of subjects to treatment groups will be the same as those for efficacy.

3.2 Analysis Period

Depending on the purpose, different analyses will be conducted on the following study periods:

1. **OLE period**. Only data in the OLE period will be included in these analyses. This OLE analysis period will be applied to all the AE analyses, and the analyses will include all subjects who were dosed in the OLE period.
2. **Placebo-controlled and OLE period**. All the data in the placebo-controlled and OLE periods will be included in these analyses. This analysis period will be applied to all efficacy analyses. The analyses will include all subjects who were dosed in the study including those who did not enroll into the OLE period.
3. **Active treatment (placebo-controlled and OLE) period**. The active treatment period is defined as the study period(s) in which a subject received BIIB092. For early start subjects, all data from placebo-controlled and OLE periods will be included. For late start subjects,

only data in the OLE period will be included. This analysis period will be applied to all safety analyses, and the analyses will include all subjects who were dosed in the study except for subjects who received only placebo in the placebo-controlled period and did not get dosed in the OLE period.

For a given output, both the analysis population and the analysis period will determine which subjects will be included. For example, the incidence table of adverse events in the OLE period will include subjects in the safety population for the OLE period, i.e., all randomized subjects who received at least one dose of study treatment in the OLE period. The incidence rate table of adverse events in the active treatment (placebo-controlled and OLE) period will include subjects in the safety population for the active treatment period, i.e., all randomized subjects who received at least one dose of treatment in the active treatment period. In this SAP we do not separately define the analysis population in each analysis period.

3.3 Baseline

Placebo-controlled and OLE period: Unless otherwise specified, baseline for the Placebo-controlled and OLE period refers to the baseline value for the PC dosing period and is defined as the most recent non-missing measurement collected prior to the first dose of study drug.

Active treatment period baseline is defined as the last non-missing measurement collected prior to the first dose of study drug received in the dosing period (PC or OLE) in which a subject first receives BIIB092. Active treatment period baseline will be used for the Active treatment (placebo-controlled and OLE) period and OLE period analyses, unless otherwise specified.

The summaries in this section will be based on the ITT population. Analysis period will be specified for each table or figure. Unless otherwise specified, summary tables will be presented by OLE treatment group.

4 STUDY SUBJECTS

4.1 Accounting of subjects

Number of subjects who completed the PC period, and number of subjects who enrolled in the OLE period will be summarized. Disposition in the OLE period will be summarized for subjects enrolled in OLE. The summary data will include number (%) of subjects dosed in the OLE period, number (%) of subjects ongoing in the OLE, number (%) of subjects who completed the treatment/study in OLE, and number (%) of subjects who discontinued treatment and/or withdrew from study in OLE. Disposition in the entire study period (PC and OLE period) will also be summarized. The summary will include number (%) of subjects randomized, number (%) of subjects dosed in each period, and number (%) of subjects who discontinued treatment and/or withdrew from study in either PC or OLE period.

4.2 Demographic and Baseline Disease Characteristics

Demographics, baseline characteristics, and medical history will be summarized for subjects enrolled in the OLE period and for subjects not enrolled in the OLE period, respectively.

4.3 Study Drug Exposure and Study Drug Compliance

A summary table of study drug exposure and compliance in the OLE period will be provided. Number of doses (BIIB092) received will be summarized as a categorical variable (categories of 1-5, 6-10, 11-15, 16-20, 21-26, 27-39, 40-52 and 53-65) as well as a continuous variable. The number of doses (BIIB092) received via home infusion will be summarized. Number of weeks on study treatment (BIIB092), calculated as (date of last dose – date of first dose +28)/7, will be summarized as a categorical variable (every 6 months for the first 2 years of OLE, and then every year) as well as a continuous variable. Percentage of study treatment taken up to the last dose, calculated as (the actual number of doses divided by the number of doses a subject is expected to take until the date of last dose)*100, will be summarized as a continuous variable. This table will be presented by OLE treatment group. A similar table will also be provided on the active treatment (PC and OLE) period in order to summarize the exposure data while subjects are on BIIB092.

4.4 Medications and Non-drug therapies

The number (%) of subjects taking concomitant medication and non-drug therapies (defined as diagnostic procedures or medical treatment procedures) in the OLE period will be summarized. In addition, number of subjects in the ITT population that have taken any concomitant medications and non-drug therapies in the active treatment (placebo-controlled and OLE) period will be summarized.

Parkinson's disease medications taken concomitantly at baseline of the placebo-controlled period are defined as Parkinson's disease medications that were being taken at the time of the first dose, i.e., started prior to the first dose and continued until after the first dose. For subjects enrolled in the OLE period, the number (%) of subjects taking Parkinson's disease medications concomitantly at the baseline of the placebo-controlled period will be summarized. A similar summary will be provided for subjects taking Parkinson's disease medication concomitantly at the baseline of the OLE period. In addition, number of subjects using Parkinson's disease medications concomitantly at baseline of the OLE period will be summarized by individual medication. Subjects who have any change in Parkinson's disease medications during the OLE period will be summarized overall and by the timing of change, i.e., the number of subjects changing between Week 52 and Week 64, the number of subjects changing between Week 64 and Week 76, etc.

4.5 Protocol Deviations

Protocol deviations identified during site monitoring will be captured in a Protocol Deviation log and categorized as key or non-key deviations based on Protocol Deviation Classification (see Appendix of the placebo-controlled SAP). Key protocol deviations that occurred in the OLE period will be summarized for subjects enrolled in the OLE. Key protocol deviations for all ITT subjects in the combined placebo-controlled and OLE periods will also be summarized.

5 EFFICACY DATA

5.1 General Considerations

The analysis population for efficacy analysis is the ITT population and data from both the placebo-controlled and OLE periods will be included. All efficacy analyses will be presented by BIIB092 late start and BIIB092 early start groups, and along with the by-visit comparison between the two groups.

There will be no multiple comparison adjustments.

5.2 Visit windows for mapping efficacy endpoint

For efficacy data that are summarized or analyzed by visit, data collected on all scheduled visits and all unscheduled visits will be mapped to an appropriate analysis visit using the windowing scheme shown in Table 1. If there are 2 or more assessments available in the same analysis window for a subject, the assessment that is closest to the target visit day will be used for analysis. If there are 2 or more assessments in the same analysis window with the same distance from the target visit day, the later assessment will be used.

Table 1 Visit Windows for Primary Endpoint: PSPRS

| Analysis visit | Target visit day | Analysis visit window |
|-----------------------|-------------------------|--|
| Baseline | 1 | Most recent non-missing value on or prior to the first dose date |
| Week 12 | 85 | [43, 126] |
| Week 24 | 169 | [127, 210] |
| Week 36 | 253 | [211, 294] |
| Week 48 | 337 | [295, 350] |
| Week 52 | 365 | [351, 378] |
| Week 64 | 449 | [407, 490] |
| Week 76 | 533 | [491, 574] |
| Week 88 | 617 | [575, 658] |
| Week 100 | 701 | [659, 742] |
| Week 112 | 785 | [743, 826] |
| Week 124 | 869 | [827, 910] |
| Week 136 | 953 | [911, 994] |
| Week 148 | 1037 | [995, 1078] |
| Week 160 | 1121 | [1079, 1162] |
| Week 172 | 1205 | [1163, 1246] |
| Week 184 | 1289 | [1247, 1330] |
| Week 196 | 1373 | >=1331 |

Table 2 (a) Visit Windows for Key Secondary Efficacy Endpoints (MDS-UPDRS, CGI, PSP cognitive composite battery and PSP-QoL) and RBANS

| Analysis visit | Target visit day | Analysis visit window |
|-----------------------|-------------------------|--|
| Baseline | 1 | Most recent non-missing value on or prior to the first dose date |
| Week 12 | 85 | [43, 126] |
| Week 24 | 169 | [127,210] |
| Week 36 | 253 | [211, 308] |
| Week 52 | 365 | [309, 378] |
| Week 64 | 449 | [407, 490] |
| Week 76 | 533 | [491, 616] |
| Week 100 | 701 | [617, 784] |
| Week 124 | 869 | [785, 952] |
| Week 148 | 1037 | [953, 1120] |
| Week 172 | 1205 | [1121, 1288] |
| Week 196 | 1373 | >=1289 |

Table 3 (b) Visit Windows for Key Secondary Efficacy Endpoint PSP cognitive composite battery (13 individual subtests)

| Analysis visit | Target visit day | Analysis visit window |
|-----------------------|-------------------------|--|
| Baseline | 1 | Most recent non-missing value on or prior to the first dose date |
| Week 12 | 85 | [43, 126] |
| Week 24 | 169 | [127,210] |
| Week 36 | 253 | [211, 308] |
| Week 52 | 365 | [309, 378] |
| Week 76 | 533 | [449, 616] |
| Week 100 | 701 | [617, 784] |
| Week 124 | 869 | [785, 952] |
| Week 148 | 1037 | [953, 1120] |
| Week 172 | 1205 | [1121, 1288] |
| Week 196 | 1373 | >=1289 |

Table 4 Visit Windows for Other Secondary Efficacy Endpoints: SEADL, Phonemic Fluency Test, WAIS-IV Letter Number Sequencing Task, Color Trails test, and MoCA

| Analysis visit | Target visit day | Analysis visit window |
|----------------|------------------|--|
| Baseline | 1 | Most recent non-missing value on or prior to the first dose date |
| Week 12 | 85 | [43, 126] |
| Week 24 | 169 | [127,210] |
| Week 36 | 253 | [211, 294] |
| Week 48 | 337 | [295, 434] |
| Week 76 | 533 | [435, 616] |
| Week 100 | 701 | [617, 784] |
| Week 124 | 869 | [785, 952] |
| Week 148 | 1037 | [953, 1120] |
| Week 172 | 1205 | [1121, 1288] |
| Week 196 | 1373 | >=1289 |

[REDACTED]

| [REDACTED] | [REDACTED] | [REDACTED] |
|------------|------------|------------|
| [REDACTED] | [REDACTED] | [REDACTED] |
| [REDACTED] | [REDACTED] | [REDACTED] |
| [REDACTED] | [REDACTED] | [REDACTED] |
| [REDACTED] | [REDACTED] | [REDACTED] |
| [REDACTED] | [REDACTED] | [REDACTED] |
| [REDACTED] | [REDACTED] | [REDACTED] |
| [REDACTED] | [REDACTED] | [REDACTED] |
| [REDACTED] | [REDACTED] | [REDACTED] |
| [REDACTED] | [REDACTED] | [REDACTED] |
| [REDACTED] | [REDACTED] | [REDACTED] |

Table 5 Visit Windows for Volumetric MRI

| Analysis visit | Target visit day | Analysis visit window |
|----------------|------------------|-----------------------|
| Baseline | 1 | <=84 |
| Week 24 | 169 | [85, 252] |
| Week 52 | 365 | [281, 448] |
| Week 100 | 701 | [617, 784] |

Table 6: Visit Windows for CSF PD analysis data

| Analysis visit | Target visit day | Analysis visit window |
|----------------|------------------|--|
| Baseline | 1 | Most recent non-missing pre-dose value |
| Week 52 | 365 | [274, 532] |
| Week 100 | 701 | >=533 |

Handling of missing items for scales

Please refer to the placebo-controlled SAP for the imputation method. The same method will be applied to efficacy endpoints collected in the OLE period.

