Monitor for Non-Serious Adverse Events (NSAEs)	Collection of NSAEs begins at initiation of study treatment and continues throughout the study and until 30 days following the last dose. Participants who discontinue study treatment should have an assessment of AEs 30 days after last dose. ^d					
Monitor for Serious Adverse Events (SAEs)	Following written consent to participate in the study, all SAEs whether related or not related to study treatment that occur during the screening period, continuously throughout the study, and until 30 days following the last dose, should be monitored and recorded. Participants who discontinue study treatment should have an assessment of SAEs 30 days after last dose. ^d					
Efficacy Assessments						
Progressive Supranuclear Palsy Rating Scale (PSPRS)			X	X	X	

CONFIDENTIAL

The information contained herein may not be used, disclosed, or published without the written consent of Biogen MA Inc.

Procedure	Week 52	Weeks 56, 60, 68, 72, 80, 84, 92, 96, 104, 108, 116, 120, 128, 132, 140, 144, 152, 156, 164, 168, 176, 180, 188, and 192 ^a . (±7 days)	Weeks 64, 88, 112, 136, 160, 184 (±7 days)	Weeks 76, 100, 124, 148, 172, 196 (±7 days)	Early Discontinuation ^b	Notes
MDS-UPDRS Part II, CGI, RBANS, PSP-QoL			See notes	X	X	At Week 64 only.
SEADL, Phonemic Fluency, Letter-Number Sequencing (LNS), Color Trails Test (CTT), MoCA				X		
██████████ ██████████				■		██████████
Magnetic resonance imaging (MRI)				See notes		At Week 100 only.
Lumbar Puncture (LP)				See notes		At Week 100 only (██████████ ██████████).
Pharmacokinetic (PK) Assessments						
Blood PK Sampling ^c		See notes		X		At Week 56 only.
CSF PK Sampling ^c				See notes		At Week 100 only (██████████ ██████████).
██████████						
██████████			██████████	■		██████████
██████████				██████████		██████████ ██████████

CONFIDENTIAL

The information contained herein may not be used, disclosed, or published without the written consent of Biogen MA Inc.

Procedure	Week 52	Weeks 56, 60, 68, 72, 80, 84, 92, 96, 104, 108, 116, 120, 128, 132, 140, 144, 152, 156, 164, 168, 176, 180, 188, and 192 ^a . (±7 days)	Weeks 64, 88, 112, 136, 160, 184 (±7 days)	Weeks 76, 100, 124, 148, 172, 196 (±7 days)	Early Discontinuation ^b	Notes
Clinical Drug Supplies						
Dispense Study Treatment	X	X	X	X		Duration of infusion will be at least 1 hour.

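### The OLE SAP gives two conflicting sets of visit windows for the PSP cognitive composite, and neither handles the Week 64 visit properly

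*SAP*

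**What the plan says.** **Windows.** OLE SAP section 5.2 has two tables that name the composite.

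- Table 2(a) is captioned "Visit Windows for Key Secondary Efficacy Endpoints (MDS-UPDRS, CGI, PSP cognitive composite battery and PSP-QoL) and RBANS". Its rows include "Week 64 | 449 | [407, 490" and "Week 76 | 533 | [491, 616" (visit, target day, window).
- Table 3(b) is captioned "Visit Windows for Key Secondary Efficacy Endpoint PSP cognitive composite battery (13 individual subtests". It goes from Week 52 [309, 378] directly to "Week 76 | 533 | [449, 616", with no Week 64 row.

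If a window holds several assessments, the same section takes the one nearest the target day.

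**Schedule.** In Protocol section 2, Table 3 (extension period, visits ±7 days), RBANS is done at Week 64, at Weeks 76, 100, 124 and so on, and at Early Discontinuation. The row "SEADL, Phonemic Fluency, Letter-Number Sequencing (LNS), Color Trails Test (CTT), MoCA" is marked only at Weeks 76, 100, 124 and so on.

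**Scoring.** Placebo-controlled SAP section 5.3.1.3 builds the composite from 11 RBANS tests, LNS and phonemic fluency, grouped in three domains. A domain score is the mean of whichever of its tests were completed, and the composite is the mean of the three domain scores. That section applies the RBANS windows to all subtests.

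**Use.** The OLE analysis is run "once all subjects have completed the PC period" (OLE SAP section 3.1). Section 5.3 lists the composite among the OLE efficacy endpoints for that analysis. Section 5.1 specifies by-visit comparisons of early start with late start and no multiplicity adjustment.

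**The concern.** Day 449 is both the target day of Week 64 and the first day of the Week 76 window in Table 3(b). A Week 64 RBANS done on time or a few days late can therefore be labelled Week 76, and one done a day early has no label at all. Table 2(a) labels the visit correctly but names the composite at a visit where two of its 13 tests are not collected.

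Two programmers working from this SAP could produce different Week 64 and Week 76 results for the composite. In a progressive disease, values taken 11 to 12 weeks early would tend to understate decline at Week 76. A composite without LNS and phonemic fluency is also a different measure from the baseline it is subtracted from, where all 13 tests are scheduled.

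**Working it through.** **1. Reproduce the bounds.** Target day = 7 × week + 1, so Weeks 52, 64, 76 and 100 fall on Days 365, 449, 533 and 701. Windows change at midpoints, and the midpoint opens the later window.

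- Without a Week 64 visit: (365 + 533)/2 = 449 and (533 + 701)/2 = 617. This is Table 3(b)'s Week 76 window, [449, 616].
- With a Week 64 visit: (365 + 449)/2 = 407 and (449 + 533)/2 = 491. These are Table 2(a)'s Week 64 and Week 76 lower bounds.

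Table 3(b) is thus arithmetically correct for a schedule with no Week 64 assessment. That suits LNS and phonemic fluency, but not the 11 RBANS subtests.

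**2. Map the permitted Week 64 days.** Day 449 ±7 is Days 442 to 456, which is 15 days.

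| RBANS done on | Table 2(a) | Table 3(b) |
|---|---|---|
| Days 442–448 (7 of 15) | Week 64 | no window (gap is Days 379–448) |
| Days 449–456 (8 of 15) | Week 64 | Week 76 |

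The records relabelled Week 76 precede its target by 533 − 456 = 77 to 533 − 449 = 84 days.

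**3. Apply the nearest-to-target rule.** A Week 76 visit within ±7 days (Days 526 to 540) is at most 7 days from Day 533. A Week 64 record is at least 77 days away, so it is never chosen when an on-schedule Week 76 RBANS exists. Relabelling is confined to participants with no Week 76 RBANS. Two groups can be foreseen:

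- participants between Weeks 64 and 76 at the interim lock;
- participants who discontinued in that interval. Early Discontinuation includes RBANS but not LNS or phonemic fluency. A discontinuation RBANS on Days 449–490 is Week 76 under Table 3(b) and Week 64 under Table 2(a).

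**4. What a Week 64 composite contains.** Without LNS and phonemic fluency, 11 of 13 tests remain. The working memory/executive domain keeps 3 of 5: semantic fluency, digit span and line orientation. Each test in that domain normally carries 1/3 × 1/5 = 1/15 of the composite. The two absent tests carry 2/15 = 13.3%. The remaining three rise from 1/15 to 1/3 × 1/3 = 1/9 each.

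**The case against.** The best defence is that Table 2(a) governs. It names the composite and RBANS, and the placebo-controlled SAP applies RBANS windows to all subtests. Table 3(b) may be meant only for subtest-level summaries, and OLE SAP section 5.3 lists the composite rather than the subtests. On that reading no Week 64 RBANS reaches the Week 76 composite. This is plausible, but the OLE SAP does not say so and does not expressly adopt the placebo-controlled windowing rule. It also leaves a Week 64 composite built from 11 tests. If instead Table 2(a) is for the composite and Table 3(b) for its components, the Week 64 composite has no subtest row to draw on.

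A reader might infer that Week 76 results in general contain data 12 weeks early. The documents do not support that: it requires Table 3(b) to govern, 7 of the 15 permitted days go nowhere, and the nearest-to-target rule protects everyone with an on-schedule Week 76 RBANS.

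A reader might also infer that many participants are affected. The documents give no enrolment curve, lock date or extension retention. They say only that too few will have reached Week 100. The 8-to-7 split counts calendar days, not participants. OLE SAP section 5.4 also lets visits with too few data be left out of the repeated-measures model.

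Finally, lines are blacked out in the composite scoring section. A minimum-test rule could lie there, so the 11-test composite rests on the visible text.

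**Conclusion.** The conflict is real and no text resolves it. Under Table 3(b), a Week 64 RBANS is either lost (Days 442–448) or used as Week 76, 77 to 84 days early (Days 449–456). The second outcome arises only for participants with no Week 76 RBANS. Their number is unknown, so the effect on the Week 76 estimate could be nil or large. Under Table 2(a), the Week 64 composite lacks 13.3% of its intended weight, assuming the blacked-out text holds no minimum-test rule.

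The point is minor. Table 2(a)'s caption calls the composite key secondary, but the extension efficacy endpoints are tertiary in the objectives table and carry no multiplicity control. The placebo-controlled Week 52 analysis is not affected.

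**What to change.** 1. In Table 3(b), start the Week 76 window at Day 491, matching Table 2(a).
2. In Table 3(b), add a Week 64 row, target Day 449, window [407, 490], for the RBANS subtests only.
3. In Table 2(a), remove the composite from the Week 64 row, so that the 13-test composite is not reported at that visit.
4. State that the Week 52 composite is kept. A blanket rule limiting the composite to visits with all 13 tests scheduled would delete it, because LNS and phonemic fluency are done at Week 48 (Day 337) and join the Week 52 RBANS through the [309, 378] window.

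The cost is a few table edits and a sentence. No visit, assessment or data collection changes. One case remains: an Early Discontinuation RBANS on Days 491–616 would still give an 11-test composite at Week 76, so the same sentence could say whether such records count.
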